2.6.5. Duration of Treatment

Duration of treatment in months is derived as last non-zero Daratumumab/Atezolizumab dosing date – first non-zero Daratumumab/Atezolizumab dosing date + 1, divided by 365.25/12.

2.6.6. Maximum number of Treatment Cycles

A subject is considered as treated in a cycle if he/she receives any nonzero dose of Daratumumab/Atezolizumab in that cycle. The maximum number of treatment cycle for each subject is the largest cycle number in which a subject receives any nonzero dose of Daratumumab/Atezolizumab.

2.6.7. Relative Dose Intensity

For Daratumumab, the relative dose intensity (%) is the ratio of total dose received (mg/kg) and total planned dose (mg/kg), calculated as the planned dose times the number of administered infusions. For Atezolizumab, the relative dose intensity (%) is the ratio of total dose received (mg) and total planned dose (mg), calculated as the planned dose times the number of administered infusions.

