6.1.2. Daratumumab Treatment Schedule and Administration

Daratumumab will be administered on Days 1, 8, and 15, for the first 3 cycles, then on Day 1 of each 21-day cycle thereafter until one or more treatment discontinuation criteria are met (eg, disease progression or unacceptable toxicity).

Daratumumab will be administered IV at 16 mg/kg. Each subject's dose will be calculated based on the subject's weight at Cycle 1 Day 1 rounded to the nearest kilogram. The dose of daratumumab will remain constant throughout the study, unless the subject's weight changes more than 10% from Cycle 1 Day 1. All infusions will be planned as outpatient visits. Subjects will receive preinfusion medications and postinfusion medications as outlined in Section 6.1.3.

The dilution volumes, initial infusion rates, and increment of infusion rates for the first, second, and subsequent doses in the absence of an infusion-related reaction >Grade 1 are provided in Table 7. The first infusion, with a volume of 1,000 mL, takes approximately 8 hours; the second and subsequent infusions, with volumes of 500 mL, take approximately 4 hours. The maximum infusion rate for all infusions is 200 mL/hour. The Sponsor may modify the infusion rates or the preinfusion medications prospectively based upon the information collected to date from this and other studies.

Table 7: Daratumumab Infusion Rates

	Dilution Volume	Initial Infusion Rate (first hour)	Incremental Increases in Infusion Rate^a	Maximum Infusion Rate
First infusion	1000 mL	50 mL/hour	50 mL/hour every hour	200 mL/hour
Second infusion^b	500 mL	50 mL/hour	50 mL/hour every hour	200 mL/hour
Subsequent infusions^c	500 mL	100 mL/hour	50 mL/hour every hour	200. mL/hour

- Consider titration of the infusion rate only in the absence of infusion reactions.
- Dilution volume of 500 mL should be used only if there were no Grade 1 (mild) or greater infusion reactions during the first 3 hours of the first infusion. Otherwise, continue to use a dilution volume of 1000 mL.
- Use a modified initial rate for subsequent infusions (ie, third infusion onwards) only if there were no Grade 1 (mild) or greater infusion reactions during a final infusion rate of ≥ 100 mL/hr in the first two infusions. Otherwise, continue to use instructions for the second infusion.

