2.6.4. Total Dose Received

For Daratumumab, total dose (mg/kg) is the sum of the administered doses per kilogram at each visit, which is calculated as the total dose (mg) recorded on the eCRF divided by body weight (kg) at that visit. For Atezolizumab, total dose (mg) is the sum of the administered doses at each visit, which is calculated as the total dose (mg) recorded on the eCRF.

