4.3. Treatment Compliance

Refer to section 4.4.

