4.4. Extent of Exposure

Duration of treatment in months will be summarized, together with the number of treatment cycles. Descriptive statistics for the total dose received, total number of infusions, and relative dose intensity (%) will be provided for Daratumumab and Atezolizumab, respectively.

The frequencies of actions planned prior to infusion start and taken during infusion will be summarized, together with reasons reported on eCRF.

For cross-over subjects, exposure data after initiation of cross-over treatment may be summarized separately, as applicable.

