6.1.1. Treatment Emergent Adverse Events

The following summaries will be provided for all TEAEs:

- An overview of TEAE will be provided, including the incidence of TEAE, serious TEAE, maximal grade of TEAE, treatment discontinuation due to TEAE, , and death due to TEAE.
- A listing of all TEAEs.

In addition, the following summaries will be generated:

- TEAEs by system organ class (SOC) and preferred term (PT)
- TEAEs by SOC, PT, and relationship to study medication
- TEAEs by SOC, PT, and grade 3/4
- Most common (at least 10%) TEAEs by SOC, PT, and grade 3/4
- TEAEs by SOC, PT, and worst grade

- Serious TEAEs by SOC and PT
- Serious TEAEs by SOC, PT, and grade 3/4
- Most common (at least 1%) serious TEAEs by SOC, PT, and grade 3/4

- Grade 3 or 4 TEAEs by SOC and PT
- Grade 3 or 4 TEAEs by SOC, PT, and relationship to study medication

The following summaries of treatment modifications due to TEAEs will be provided:

- Infusion delay due to TEAE by SOC, PT and relationship to study medication

- Infusion skipped due to TEAE by SOC, PT and relationship to study medication
- Infusion interruption due to TEAE by SOC, PT and relationship to study medication
- Infusion rate decreased due to TEAE by SOC, PT and relationship to study medication
- Infusion aborted due to TEAE by SOC, PT and relationship to study medication

In addition, the following summaries will be generated:

- Study drug discontinuation due to TEAEs by SOC, PT, and grade 3/4
- Treatment discontinuation due to TEAEs by PT and grade 3/4
- Death due to TEAEs by PT and grade 3/4

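### SAP relative dose intensity divides by the infusions actually given, so omitted doses of either drug do not count as lost exposure

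*SAP*

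**What the plan says.** SAP 2.6.7 makes RDI the ratio of total dose received to total planned dose. For daratumumab the denominator is "total planned dose (mg/kg), calculated as the planned dose times the number of administered infusions". The atezolizumab rule is the same, in mg. SAP 2.6.4 builds the numerator from administered doses only; for daratumumab each one is "calculated as the total dose (mg) recorded on the eCRF divided by body weight (kg) at that visit".

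SAP 4.4 reports the result: descriptive statistics for "total dose received, total number of infusions, and relative dose intensity (%) will be provided for Daratumumab and Atezolizumab, respectively". It also summarises duration of treatment, number of cycles, and infusion actions with reasons. SAP 4.3 on treatment compliance says only "Refer to section 4.4". SAP 2.6.6 takes the cycle count as "the largest cycle number in which a subject receives any nonzero dose". SAP 6.1.1 adds tables such as "Infusion skipped due to TEAE by SOC, PT and relationship to study medication" and "Infusion delay due to TEAE by SOC, PT and relationship to study medication".

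On the protocol side, Sections 6.1.4 and 6.2 allow no dose modification of either drug. Sections 6.1.5 and 6.2 class a dose not started within its window as missed and do not replace it. Section 6.1.2 sets the daratumumab dose on Cycle 1 Day 1 weight, rounded to a whole kilogram, and adds: "The dose of daratumumab will remain constant throughout the study, unless the subject's weight changes more than 10% from Cycle 1 Day 1".

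**The concern.** RDI is normally read as how much of the intended dose a subject received over the treatment period. Here the denominator shrinks with every infusion that is not given, so the ratio measures only how complete the given infusions were. Doses may not be reduced and missed doses are not replaced, so omission is one of the main ways dose is lost, and the ratio is not built to register it.

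What is at stake is the description of exposure, mainly in Arm B. The protocol records that the monitoring committee saw no benefit from the combination. A reader of the study report will ask how much daratumumab was delivered, and could take an RDI near 100% as near-complete delivery whether or not that was so.

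A second, smaller matter concerns daratumumab alone: the numerator uses a different body weight from the one that set the dose.

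**Working it through.** The documents state no RDI value, so there is no figure to reproduce. The check applies the SAP formula to the protocol schedule.

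**Inputs.** Daratumumab is 16 mg/kg on Days 1, 8 and 15 of Cycles 1 to 3, then Day 1 of each cycle (Protocol 6.1.2): 3 × 3 + 3 = 12 infusions through Cycle 6. Atezolizumab is 1,200 mg once per cycle (Protocol 6.2): 6 infusions through Cycle 6.

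**Formulas.**
- SAP RDI = sum of doses given / (planned dose × infusions administered).
- Delivered over scheduled = sum of doses given / (planned dose × infusions scheduled).

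**Omissions, with full infusions and visit weight equal to dosing weight.**

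| Case | SAP RDI | Delivered / scheduled |
|---|---|---|
| Daratumumab, 11 of 12 | 11/11 = 100% | 11/12 = 91.7% |
| Daratumumab, 10 of 12 | 10/10 = 100% | 10/12 = 83.3% |
| Daratumumab, 9 of 12 | 144/144 mg/kg = 100% | 144/192 mg/kg = 75.0% |
| Atezolizumab, 4 of 6 | 4/4 = 100% | 4/6 = 66.7% |

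The three daratumumab misses are taken as non-consecutive, because Protocol 6.1.5 requires permanent discontinuation after three or more consecutive misses for adverse events.

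**Ordering.** A subject who misses nothing but has one daratumumab infusion half given scores 11.5/12 = 95.8%. That ranks below the subject who missed three and scores 100%.

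**Omission combined with a partial infusion.** Atezolizumab with one half infusion in six scores 5.5/6 = 91.7%. If a full dose is also skipped, SAP RDI is 4.5/5 = 90.0%, while delivered over scheduled is 4.5/6 = 75.0%. RDI moves, but the movement does not measure the missed dose.

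**Weight (daratumumab only).** Ignoring rounding, an infusion given exactly as directed scores 1/1.10 = 90.9% after a 10% gain and 1/0.90 = 111.1% after a 10% loss. Rounding the dosing weight moves these slightly: at 60.4 kg with no weight change, 60/60.4 = 99.3%. So these figures are illustrations, not limits. Over a course the effect is smaller. The documents give no weight trajectory, so assume a steady change to day 105 across dose days 0, 7, …, 56, 63, 84 and 105, again ignoring rounding. The mean of 1/(relative weight) is then 100.8% to 103.4% for a loss of 2% to 8%, and 99.2% to 96.95% for a gain of 2% to 8%.

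**The case against.** The strongest reply is that the SAP prints its formula openly and that missed doses appear elsewhere. SAP 4.4 reports total dose, infusion counts, cycles, duration of treatment and infusion actions with reasons, and those actions are not limited to adverse events. SAP 6.1.1 adds skips and delays due to treatment-emergent events. With a fixed schedule, duration and infusion counts let a reader gauge delivery roughly. Site staff give every infusion (Protocol 7), so sending compliance to the exposure section is reasonable.

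Much of that stands: omissions are partly disclosed, and the cross-reference for compliance is no fault in itself. What does not stand is that these outputs replace the missing ratio. None has a scheduled-dose denominator. The cycle count is the largest cycle reached, so a cycle with no dose in the middle of treatment disappears. Duration of treatment ends at the last non-zero dose (SAP 2.6.5), so misses just before discontinuation disappear too. RDI remains the only output that sets delivered against planned dose.

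A reader might go further and infer any of the following; the documents support none of them.
- RDI is always exactly 100%, or an omission can never shift it. Partial infusions and weight differences move it.
- The SAP conceals missed doses. The outputs just listed show them in part.
- Daratumumab was under-delivered in Arm B. The documents contain no exposure data.

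**Conclusion.** The point holds and is minor. As defined, RDI for both drugs is the mean percent of planned dose per infusion given, and it does not count omitted infusions. In the worked cases it reads 100% where delivery against schedule is 75.0% (daratumumab, 9 of 12) or 66.7% (atezolizumab, 4 of 6). Those figures assume full infusions and, for daratumumab, visit weight equal to dosing weight.

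Separately, the weight mismatch lets a correctly given daratumumab infusion score roughly 10% either side of 100%.

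No test, endpoint or analysis set uses RDI. The response-rate analysis and every other efficacy result are unaffected.

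**What to change.** Use one definition per drug in SAP 2.6.7.

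- **Denominator.** Total planned dose = protocol dose × (infusions administered + planned infusions not given for any reason). The second term includes doses that the protocol classes as missed because they fell outside the window. Missed doses enter the numerator as zero. An infusion given late is counted once, as administered.
- **Period.** Count from first dose to the earliest of that drug's discontinuation, the first crossover dose and the data cutoff. The end point must be set for each drug, because Arm B subjects may stop one agent and stay on the other (Protocol 3.1). Running the count to discontinuation captures trailing misses: if the last 2 of 12 are missed, the result is 10/12 = 83.3%, not 100%.
- **Weight.** Compute daratumumab mg/kg with the weight used to set the dose.
- **Reconciliation.** Protocol 6.1.5 both treats a daratumumab dose outside its window as missed and, for delays beyond 5 days in Cycles 2 to 20, requires later dates to be adjusted. These statements must be reconciled, and the SAP should apply the reconciled rule to this count.

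The cost is SAP wording and one derived variable per drug. It assumes that the eCRF identifies infusions not given whatever the reason; SAP 4.4 and 6.1.1 suggest this but do not establish it. If the eCRF cannot, keep the current ratio and rename it *mean percent of planned dose per administered infusion*. The downside is that reported RDI will be lower.

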2.6.8. End of Follow-up and Duration of Follow-up

The end of follow-up is the date of death for subjects who died. For those who still alive, the end of follow-up is defined as the maximum date of the following study evaluations: labs (hematology, chemistry, serology, coagulation, thyroid function), adverse events, vital signs, ECOG performance status, study drug administration, 12-lead ECG, disposition, pre-infusion medications, post-infusion medications, concomitant medications, Subsequent anti-cancer treatment, tumor assessment, clinical events/disease response per investigator and date of last known to be alive.

Duration of follow-up (in months) equals the end of follow-up minus the first dose date plus 1, divided by 365.25/12.

2.6.9. Relationship of Adverse Events to Study Medication

For each adverse event, its relationship to study medication is determined by investigator and recorded on the eCRF. An adverse event is considered as related to study medication if the relationship is possible, probable or very likely.

2.6.10. Treatment Emergent Adverse Events

Treatment emergent adverse events (TEAEs) are defined as any AE with onset date and time on or after that of the first dose through 30 days after the last study drug administration, or the day prior to start of subsequent therapy, whichever is earlier; or any AE that is considered related to (very likely, probably, or possibly related) study medication regardless of the start date of the event. AEs with missing or partial onset date and time will be considered as treatment-emergent unless the onset date and time of an AE can be determined as earlier than that of the first dose, or later than 30 days after last study drug administration.

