11.8. Safety Analyses

Adverse Events

The verbatim terms used in the CRF by investigators to identify adverse events will be coded using the Medical Dictionary for Regulatory Activities (MedDRA). Treatment-emergent adverse events are AEs with onset during the treatment phase or that are a consequence of a pre-existing condition that has worsened since baseline. All reported adverse events will be included in the analysis. For each adverse event, the percentage of subjects who experience at least 1 occurrence of the given event will be summarized by treatment group. In addition, comparisons between treatment groups will be provided if appropriate.

Summaries, listings, datasets, or subject narratives may be provided, as appropriate, for those subjects who die, who discontinue treatment due to an adverse event, or who experience a severe or a serious adverse event.

Clinical Laboratory Tests

Laboratory data will be summarized by type of laboratory test. Reference ranges and markedly abnormal results (specified in the Statistical Analysis Plan) will be used in the summary of laboratory data. Descriptive statistics will be calculated for each laboratory analyte at baseline and for observed values and changes from baseline at each scheduled timepoint. Changes from baseline results will be presented in pre- versus posttreatment cross-tabulations (with classes for below, within, and above normal ranges). A listing of subjects with any laboratory results outside the reference ranges will be provided. A listing of subjects with any markedly abnormal laboratory results will also be provided.

Parameters with predefined NCI-CTCAE toxicity grades will be summarized. Change from baseline to the worst adverse event grade experienced by the subject during the study will be provided as shift tables.

Electrocardiogram

Electrocardiogram data will be summarized based on categories of normal, abnormal either clinically significant or not clinically significant and listed.

Vital Signs

Descriptive statistics of temperature, pulse/heart rate, and blood pressure (systolic and diastolic) values and changes from baseline will be summarized at each scheduled timepoint. The percentage of subjects with values beyond clinically important limits will be summarized.

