12.1. Definitions

12.1.1. Adverse Event Definitions and Classifications

Adverse Event

An adverse event is any untoward medical occurrence in a clinical study subject administered a medicinal (investigational or non-investigational) product. An adverse event does not necessarily have a causal relationship with the treatment. An adverse event can therefore be any unfavorable and unintended sign (including an abnormal finding), symptom, or disease temporally associated with the use of a medicinal (investigational or non-investigational) product, whether or not related to that medicinal (investigational or non-investigational) product. (Definition per International Conference on Harmonisation [ICH]).

This includes any occurrence that is new in onset or aggravated in severity or frequency from the baseline condition, or abnormal results of diagnostic procedures, including laboratory test abnormalities.

Note: The Sponsor collects adverse events starting with the signing of the ICF (refer to Section 12.3.1, All Adverse Events, for time of last adverse event recording).

Serious Adverse Event

A serious adverse event based on ICH and EU Guidelines on Pharmacovigilance for Medicinal Products for Human Use is any untoward medical occurrence that at any dose:

- Results in death
- Is life-threatening
(The subject was at risk of death at the time of the event. It does not refer to an event that hypothetically might have caused death if it were more severe.)
- Requires inpatient hospitalization or prolongation of existing hospitalization
- Results in persistent or significant disability/incapacity
- Is a congenital anomaly/birth defect
- Is a suspected transmission of any infectious agent via a medicinal product
- Is Medically Important.*

*Medical and scientific judgment should be exercised in deciding whether expedited reporting is also appropriate in other situations, such as important medical events that may not be immediately life threatening or result in death or hospitalization but may jeopardize the subject

or may require intervention to prevent one of the other outcomes listed in the definition above. These should usually be considered serious.

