6.1. Adverse Events

Unless otherwise specified, only TEAEs will be summarized.

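### The SAP's treatment-emergent definition omits the protocol's worsening limb, so a pre-dose AE that worsens on treatment can miss the AE tables if kept as one unrelated record

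*SAP*

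**What the plan says.** Protocol Section 11.8 defines treatment-emergent adverse events (TEAEs) as "AEs with onset during the treatment phase or that are a consequence of a pre-existing condition that has worsened since baseline". That is two limbs: onset on treatment, or worsening. The same section adds: "All reported adverse events will be included in the analysis".

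SAP Section 2.6.10 also has two limbs, but a different pair. The first is "any AE with onset date and time on or after that of the first dose through 30 days after the last study drug administration", cut off at the day before subsequent therapy if that comes sooner. The second is "any AE that is considered related to (very likely, probably, or possibly related) study medication regardless of the start date of the event". Events with a missing or partial onset default to treatment-emergent unless they can be placed before first dose or more than 30 days after the last dose. No worsening limb appears in this section or elsewhere in the SAP.

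SAP Section 6.1 then states: "Unless otherwise specified, only TEAEs will be summarized". The general AE listing in Section 6.1.1 is likewise a listing of TEAEs.

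On collection, Protocol Section 12.1.1 says: "The Sponsor collects adverse events starting with the signing of the ICF". Under Protocol Section 4, main-study consent may be signed up to 56 days before first dose.

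**The concern.** Events that start during screening are in the database, and the protocol intends those that get worse on treatment to count. The SAP's onset limb looks only at when the event began. An investigator who keeps a screening event open and raises its grade after dosing leaves a pre-dose onset date on the record, and under the SAP that record is not treatment-emergent unless it is judged related.

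Such cases are plausible here. The population has previously treated advanced lung cancer, and Protocol Attachment 4 lists cough, dyspnea, chest pain and pneumonia among the anticipated events of the disease. Safety of the combination is the first-listed secondary objective, and Protocol Section 1.4 reports that the DMC saw numerically more deaths in the combination arm. The serious, Grade 3/4 and death-due-to-TEAE tables all depend on this flag.

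The relatedness limb can bring such an event back, but the investigator makes that judgement (SAP Section 2.6.9) knowing the treatment arm. Capture of worsened pre-dose events could therefore differ between arms. The protocol's worsening limb does not depend on attribution.

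**Working it through.** The plan gives no figure to reproduce. The check compares the two definitions and follows one event through them.

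**Example.** An AE starts in screening at Grade 1 and reaches Grade 3 after first dose.

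1. *One record, known pre-dose onset, judged unrelated.* Protocol 11.8: treatment-emergent, as a pre-existing condition that worsened. SAP 2.6.10: not treatment-emergent, because onset precedes first dose and the relatedness limb is not met. It is absent from the Section 6.1.1 tables and the TEAE listing.
2. *Worsening entered as a new record dated after first dose.* Treatment-emergent under both documents.
3. *One record, judged possibly, probably or very likely related.* Treatment-emergent under the SAP whatever its date.
4. *One record, onset missing or partial and not determinable as outside the window.* Treatment-emergent under the SAP by default.

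The definitions give different answers only on path 1.

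**What still shows the event on path 1.** SAP Section 6.2 summarises and lists every death on study with its primary cause, without a TEAE filter. SAP Section 6.3 tabulates shifts from baseline grade to worst on-treatment grade for laboratory parameters. A fatal outcome or a laboratory worsening is therefore still visible. A worsening symptom such as dyspnea has no equivalent output.

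**Which path applies.** Neither document says whether a grade increase in an open screening AE creates a new record or stays under the existing onset date.

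**Size per subject.** The planned arm is 90/2 = 45 subjects (Protocol Section 11.2). The third DMC review, on which the clinical study report is to be based, had 44 per arm (Protocol Sections 1.4 and 3.2).

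- 1/45 = 2.2 percentage points
- 1/44 = 2.3 percentage points

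This is the most that one subject can move one row of an arm's incidence table. The row does not change if the subject has another qualifying TEAE in it.

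**The case against.** The strongest reply is that the protocol already treats the worsening as an AE in its own right. Section 12.1.1 includes in its AE definition an occurrence aggravated from the baseline condition. Table 1 asks sites to put new or worsened clinically significant examination and ECG findings on the AE form, and Section 9.7 asks for clinically relevant changes to be recorded there. A worsening entered that way has a post-dose onset and meets the SAP's first limb. For conditions held as medical history, the two definitions then largely agree. The recording convention may also sit in the CRF completion guidelines (Protocol Section 15), which are not among the documents.

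Much of this stands. A reader might infer that every worsened screening AE drops out of every AE table unless called related. The documents do not support that: paths 2 and 4 above also bring the event in. Nor do they support an inference that deaths go unreported, since SAP Section 6.2 covers all of them; only the attribution in the death-due-to-TEAE tables could change.

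The reply does not remove the mismatch. Section 12.1.1 says what an AE is; it does not say that an event already on record gets a new onset date when its grade rises. The protocol contains 12.1.1 and still writes the worsening limb into 11.8. Section 11 leaves specific details to the SAP, but dropping a limb is more than detail, and the SAP gives no reason for it. If sites follow different conventions, identical events would be counted differently.

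**Conclusion.** The SAP departs from the protocol's definition, and because the AE outputs are restricted to TEAEs, the departure can remove events from them. The omission requires four conditions together: onset between consent and first dose, worsening after first dose, a single record with a known pre-dose onset, and a judgement of unrelated. Where they hold, the event is missing from the AE tables, including the serious, Grade 3/4 and death-due-to-TEAE tables, and from the TEAE listing.

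Each affected subject is worth at most about 2.2 to 2.3 points of an arm's incidence. The documents give no rate of screening AEs that later worsen and no account of how they are recorded, so no number of subjects can be derived.

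A reader might also infer a bias towards counting more events in Arm B, which has two candidate drugs for attribution against one in Arm A. That direction is plausible but not shown. Screening AEs arise before treatment in both arms, and no figure shows that relatedness is assigned unequally to pre-dose events. The supportable statement is that capture could differ between arms. This is a correctable mismatch, not a defect that invalidates the safety analysis.

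**What to change.** Make three changes.

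1. Add a third limb to SAP Section 2.6.10: *or any AE with onset before first dose that increases in toxicity grade on or after first dose within the same window*. This aligns the SAP with Protocol Section 11.8. It is an operational version of the protocol's wording, which does not itself refer to toxicity grade.
2. State whether a grade increase in an AE already open before first dose is entered as a new record or kept under its existing onset date.
3. Add a listing of AEs classed as not treatment-emergent, so that excluded events can be inspected. This also narrows the gap with the protocol's statement that all reported AEs enter the analysis.

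The cost is one derivation and one listing, and AE counts may rise slightly. The derivation needs either a date of worsening or a new-record convention in the eCRF, and the documents do not say that either exists. Protocol Section 9.3 ends data collection at database lock, so what was captured should be checked first. If sites already enter worsenings as new records, the tables will not change and the added limb simply documents the practice.
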